## ABSTRACT

### **Background:**

Oral health is essential for overall wellbeing, particularly for those with chronic conditions like Diabetes Mellitus. Individuals with Diabetes face a higher risk of developing oral health complications, yet many lack adequate knowledge and proper practices to manage their oral health. Social media offers a potential platform for health education and can improve health behaviors. However, the effectiveness of using theory-based education, such as the Health Belief Model, through platforms like WhatsApp to improve oral health knowledge and behavior among individuals with diabetes remains underexplored.

### **Objectives:**

This study aims to evaluate the effectiveness of a HBM based educational intervention delivered through WhatsApp in enhancing oral health knowledge and behaviors among individuals with Type 2 diabetes, compared to a control group receiving oral health education through educational brochure.

### **Methods:**

This study utilized a quantitative randomized controlled trial approach with an intervention group and a control group. The Data were collected at baseline and one-month post-intervention. The intervention group was provided with oral health education through WhatsApp videos based on the HBM, while control group received an educational brochure. Participants' oral health knowledge and behaviors were evaluated using a detailed questionnaire. Statistical analysis was performed to evaluate changes in the knowledge and behaviors of both groups over the study period.

**Key Words:** Diabetes Mellitus, oral health, Health Belief Model, WhatsApp, knowledge, behaviors, educational intervention, social media

## INTRODUCTION

### Background

Diabetes Mellitus is a chronic metabolic disease characterized by hyperglycemia which is caused by a defect in insulin secretion, function, or both. This condition often leads to complications such as retinopathy, kidney failure, coronary artery disease, poor wound healing, foot numbness, as well as oral diseases.(1,2). Even though there are no particular oral lesions linked to diabetes mellitus but persistent uncontrolled hyperglycemia can produce oral symptoms like burning in the oral mucosa, xerostomia, dental caries, and periodontal disease (gingivitis and periodontitis), which can lead to tooth loss. Diabetes and periodontitis exhibit a bidirectional relationship, where each condition can exacerbate the other.(3) Interestingly diabetes can also be screened for using periodontal disease. According to intervention studies, treating periodontal disease may help glycemic control of individuals with diabetes and, eventually, their general health.(4)

As of 2019, there were 463 million people worldwide with Diabetes Mellitus, or 9.3% of the total population. It is predicted that this percentage will increase drastically to 10.9% (or 700 million people) by 2045.(5) Pakistan holds the third position in global diabetes prevalence. In Pakistan, more than 19 million people have diabetes.(6)

A recent study conducted in Pakistan found that while most individuals with diabetes were aware of other complications of diabetes, such as foot ulcers and retinopathy, very few participants were aware of the oral manifestations. This could be caused by the failure of the doctors to provide oral health counseling or by patients' carelessness with regard to routine dental checkups.(4) WHO states that the mainstay of diabetes therapy is education. Indeed, studies have demonstrated that education is useful in controlling diabetes, and that appropriate educational training can lower 80% of diabetic complications.(7)

According to research, although oral health education increases knowledge, it rarely results in long-lasting behavioral changes. The limited success of traditional health education has raised concerns about the knowledge-attitude-practice model, which has led to an investigation of psychological theories in an effort to better explain health behaviors.(8) One of the earliest behavior analytic models, The Health Belief Model has been applied to many studies on health

behaviors, including type 2 diabetic mellitus (T2DM).(7) At present HBM is one of the most extensively adopted theories used to develop health behavior modifying interventions .(9) The HBM, was formulated by social psychologists in the 1950s, its purpose was to understand and predict individuals' engagement in preventive health behaviors. According to this model, to incorporate improved oral health practices, Individuals with diabetes must first perceive themselves as susceptible to oral complications and recognize the severity of these complications. Additionally, they should understand the benefits of oral healthcare and have the self-efficacy to overcome the barriers, while also being influenced by internal and external cues to action that inspire them to prioritize oral health. (7)

Digital technological advancements, especially social media, have revolutionized public health communication. These platforms are useful for promoting public health since they are accessible, cost effective, and improve retention of information. Patients, particularly those with diabetes, can interact, exchange stories, and enhance their self-management using social media.(10)

## **Significance of the problem**

Oral health receives limited attention in diabetes management, despite the fact that diabetes contributes to serious oral health complications. The purpose of this study is to use an educational intervention based on HBM to improve oral health awareness which encourage healthy behaviors among individuals with diabetes. Although HBM has been effectively used in earlier studies to improve health outcomes, this study intends to investigate its efficacy via social media, specifically WhatsApp. WhatsApp enables the easy, accessible and engaging communication which makes it an important delivery platform. This study aims to assess the effectiveness of an intervention (educational content delivered via WhatsApp) in improving oral health knowledge among individuals with T2DM.

## **Objectives of the study**

The objectives of the study are to evaluate the impact of a WhatsApp-based HBM intervention on oral health knowledge and behavior of individuals with T2DM and to compare the effectiveness of WhatsApp based education with the education given via brochures.

## **Hypothesis**

Adults having T2DM who acquire HBM based educational intervention regarding oral health through WhatsApp will show a significant improvement in oral health knowledge and behaviors, as compared to those who receives the educational brochure.

## **Operational Definitions**

### **Oral Hygiene-Related Behaviors:**

Participants' reported frequency and quality of oral health practices, including brushing, flossing, gingival health, and dental visits, measured on a scale of 0(never) to 4(always) using performance related questions. Higher scores will indicate better oral hygiene related behaviors. Pre and post intervention scores were compared, and cutoff levels were determined using the mean and standard deviation (SD).(7)

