### **Perceived Susceptibility:**

How much diabetic patients think they might get oral health complications, measured using a Likert scale. (1 = Strongly Disagree to 5 = Strongly Agree). Higher scores reflect a greater perceived susceptibility. Pre and post intervention scores were compared, with cutoff levels based on the mean  $\pm$  SD. (7)

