### **Perceived Severity:**

Participants' perceptions of the severity of oral health complications and their potential impact on their overall wellbeing and diabetes management. Assessed through Likert scale statements rated from 1 (Strongly Disagree) to 5 (Strongly Agree). Higher scores indicate greater perceived severity. Pre and post scores will be compared using the mean and SD as cutoff criteria.(7)

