### **Perceived Benefits:**

Participants' beliefs about the positive outcomes of engaging in oral hygiene behaviors, such as prevention of oral complications. Assessed using Likert-scale items from 1 (Strongly Disagree) to 5 (Strongly Agree). Higher scores reflect

stronger perceived benefits. Pre and post intervention scores will be compared, and categorization will be done using the mean and SD. (7)

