**Awareness:**

The participant's knowledge about the relationship between diabetes and oral health issues, assessed through binary questions (Yes = 1, No = 0). Higher scores reflect higher awareness levels. Pre and post awareness scores will be compared, and cutoff scores will be calculated using the mean and SD. (7)

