## **Scoring**

The awareness questions section was scored such that each correct answer received 1 point, and each incorrect answer received 0 points. The total score for the awareness section was calculated based on maximum score of 10. The HBM constructs were assessed using five-point Likert scale, with response options ranging from "strongly agree" to "strongly disagree" and scored from 1 to 5, respectively. The scores for each model construct were calculated and reported within the range of 1 to 5. Similarly, the behavior questions were scored on a 5-point Likert scale of behavior evaluation, with responses ranging from "never" to "always" and scored from 0 to 4. In this study, higher scores indicate higher levels of awareness, perceived susceptibility, perceived severity, perceived benefits, perceived barriers, cues to action, self-efficacy, and performance of oral hygiene practices among diabetic patients.

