## **Data Analysis Procedure**

Data were analyzed through a statistical package for Social Sciences (SPSS) version 26. Frequency and percentages were reported for qualitative variables. Mean and standard deviations were reported for normally distributed quantitative variables while median and interquartile ranges were reported for non-normally distributed quantitative variables. Normality of quantitative variables were assessed using Shapiro-wilk's test of normality. The Independent sample t-test was conducted to compare the mean scores of perceived barriers and behavior between the intervention and control groups. For all other constructs, which were not normally distributed, the Mann-Whitney U test was applied. For within-group comparisons of pre and post scores of behaviors and perceived barriers, the Paired sample t-test was used. The Wilcoxon signed rank test, was used for the remaining variables that were not normally distributed. Stratification was carried out based on gender, diabetes duration, and education level to see the effect of these modifiers on outcome (control vs. intervention) using Chi-square test. A p value less than and equal to 0.05 was considered as significant.

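### The mean/SD cut-offs set for every outcome have no stated source, occasion or arm, and some readings would hide or distort change in the categorical summaries and, probably, the modifier analysis

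*Combined protocol and SAP*

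**What the plan says.** The Operational Definitions give each of the eight outcomes (behaviours, six Health Belief Model constructs, awareness) a cut-off based on the mean and SD. The wording varies:

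- Behaviours: "Pre and post intervention scores were compared, and cutoff levels were determined using the mean and standard deviation (SD".
- Perceived susceptibility: "Pre and post intervention scores were compared, with cutoff levels based on the mean", plus or minus the SD.
- Perceived severity: "Pre and post scores will be compared using the mean and SD as cutoff criteria".
- Perceived benefits: "Pre and post intervention scores will be compared, and categorization will be done using the mean and SD".
- Awareness: "Pre and post awareness scores will be compared, and cutoff scores will be calculated using the mean and SD".

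The definition of cues to action, like that of severity, makes the cut-off classification the means by which pre and post scores are compared. Each definition cites reference 7, but no cut-off value is given. The Scoring section defines numerical scores only.

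The Data Analysis Procedure works on scores for its main tests. For two outcomes, "The Independent sample t-test was conducted to compare the mean scores of perceived barriers and behavior between the intervention and control groups". The other constructs are compared by Mann-Whitney, and within-arm change is tested by paired t-test or Wilcoxon. The exception is the stratified analysis by gender, diabetes duration and education, which is done "to see the effect of these modifiers on outcome (control vs. intervention) using Chi-square test". The categorical outcome for that test is not defined.

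**The concern.** A cut-off taken from the data it classifies moves with those data. If the mean and SD are recalculated after the intervention, a participant must do better than the new average to count as high, so real improvement may not register. A reader of the results would expect a statement about the share with good behaviour or awareness to describe change against a fixed standard.

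Two outputs are at stake: any categorical pre-post comparison of the kind described for severity and cues to action, and the modifier analysis, if its chi-square test uses these categories. Splitting a score into two or three groups also discards information under every reading of the rule, in a trial of 98 people.

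**Working it through.** **Inputs.** The documents give 49 participants per arm, two occasions and the mean/SD rule. They give no category percentages to reproduce. Assumed for illustration: normal scores with the same SD in both arms at baseline, everyone in an arm gaining the same amount, and *high* meaning above mean + SD. Scores are in baseline SD units with baseline mean 0.

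**Formula.** Let m be the average of the group means in the pool that sets the cut-off, and v the variance of those group means. The cut-off is c = m + √(1 + v). A group with gain g has a high share of 1 − Φ(c − g).

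**Four readings of the rule.**

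1. *Per arm and occasion.* m = g and v = 0, so c − g = 1 and the share is 1 − Φ(1) = 15.9% for any g.
2. *Per occasion, arms pooled.* With gains 1 and 0 after the intervention, m = 0.5, v = 0.25 and c = 0.5 + √1.25 = 1.618. Intervention: 1 − Φ(0.618) = 26.8%. Control: 1 − Φ(1.618) = 5.3%.
3. *Fixed at pooled baseline.* c = 1. A gain of 1 gives 1 − Φ(0) = 50%. A gain of 0.5 gives 1 − Φ(0.5) = 30.9%.
4. *One cut-off from pooled pre and post data.* With group means 0, 0, 1 and 0, m = 0.25, v = 0.1875 and c = 0.25 + √1.1875 = 1.340. Intervention: 9.0% before and 1 − Φ(0.340) = 36.7% after. Control: 9.0% at both.

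| Cut-off | Gains in SD (intervention, control) | Intervention high, pre to post | Control high, pre to post |
|---|---|---|---|
| Per arm and occasion | any | 16% to 16% | 16% to 16% |
| Per occasion, arms pooled | 1, 1 | 16% to 16% | 16% to 16% |
| | 1, 0 | 16% to 27% | 16% to 5% |
| | 1, 1/3 | 16% to 24% | 16% to 8% |
| Fixed at pooled baseline | 1, 1 | 16% to 50% | 16% to 50% |
| | 1, 0 | 16% to 50% | 16% to 16% |
| | 1, 1/3 | 16% to 50% | 16% to 25% |
| One cut-off, pooled pre and post | 1, 1 | 5% to 27% | 5% to 27% |
| | 1, 0 | 9% to 37% | 9% to 9% |
| | 1, 1/3 | 8% to 34% | 8% to 14% |

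A simulation with 49 per arm and 4,000 runs (baseline mean 2.0, SD 0.6) gives the same rounded figures. The rows with gains of 1 and 1/3 matter because the control arm also receives education: it improves, yet under the second reading it seems to get worse.

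**The document's own figures, per arm.** The Sample Size section quotes post-intervention susceptibility of 4.09 (SD 0.49) and 3.64 (SD 1.01) from the cited trial. Per-arm upper cut-offs would be 4.09 + 0.49 = 4.58 and 3.64 + 1.01 = 4.65. Lower cut-offs would be 4.09 − 0.49 = 3.60 and 3.64 − 1.01 = 2.63. A score of 3.5 would be low in the intervention arm and middle in the control arm.

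**Cost of categorising.** In the same simulation setting, with a true post-intervention difference of 0.3 points (0.3/0.6 = 0.5 SD), 49 per arm, a 0.05 level and cut-offs pooled over arms, power is:

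- 69% for the t-test on scores;
- 52% for chi-square with a cut at the mean;
- 44% for chi-square with three categories.

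These figures are for an overall between-arm comparison. They show what categorising loses and are not the power of the modifier analysis.

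**The case against.** The strongest answer is that the trial's effect tests never touch the categories. This stands: every between-arm and within-arm test named in the Data Analysis Procedure uses scores, so the hypothesis is tested on scores. A reader might infer that the main results are biased toward no difference, but the documents do not support that.

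A reader might also infer that the cut-offs certainly come from this trial's own pre and post scores and so must move with the effect. The text does not say so. It cites reference 7 and leaves the source open, and baseline-fixed cut-offs are one permitted reading. Under these, or under one cut-off from pooled pre and post data, improvement shows. Nor does recalculation always shrink the between-arm contrast. With arms pooled at each occasion and gains of 1 and 0, the post-intervention odds ratio is (0.268/0.732)/(0.053/0.947) ≈ 6.5, against (0.500/0.500)/(0.159/0.841) ≈ 5.3 with baseline-fixed cut-offs. The distortion there lies in each arm's change over time.

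The link to the chi-square test is likewise probable, not proven. Awareness items are binary and behaviour items have five ordered responses, so single items could be tabulated. The bracketed phrase about control and intervention could even mean cross-tabulating arm against the modifiers. Still, the mean/SD cut-offs are the only categorisation defined for the scale scores.

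Finally, the Data Analysis Procedure calls every construct except barriers and behaviour non-normal, so the normal-theory percentages are illustrative for most outcomes.

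None of this removes the gap. Two definitions make the cut-offs the basis of the pre-post comparison, and the rule cannot be applied as written without further choices that change the answer.

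**Conclusion.** The concern holds in limited form. The source, occasion, pooling and number of categories of the mean/SD cut-offs are undefined for all eight outcomes, and the readings give materially different pictures of the same data: for a 1 SD gain in the intervention arm alone, that arm's high share goes from 16% to 16%, 27% or 50%, or from 9% to 37%. Complete masking needs recalculation per arm and occasion, or per occasion on pooled arms with similar gains in both.

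The percentages rest on normal scores and a cut at mean + SD. The invariance under per-arm recalculation does not need normality: it holds for any distribution that shifts without changing shape. The exposure is limited to categorical summaries and, on the likeliest reading, the chi-square modifier analysis. For the modifier analysis, scores are the better basis under every reading, because categorising loses power even when the cut-offs are fixed.

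**What to change.** 1. In the Data Analysis Procedure, replace the chi-square test with an analysis of gender, education and diabetes duration on the continuous scores, for example a model with an arm-by-modifier term, reported as an estimate with its confidence interval. For scores judged non-normal, use a bootstrap or robust interval.
2. In the Operational Definitions, remove the mean/SD cut-offs from the pre-post comparisons. If categories are wanted for description, calculate one cut-off per score from the pooled baseline data of both arms, apply it unchanged to both arms at both occasions, and state the number of categories.
3. If analyses have already been run on categories, report the change openly.

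The cost is some wording and a recode of data already collected. Locally defined high/low labels are lost from the comparisons. With 98 participants the modifier estimates will still be imprecise, and the report should say so.

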### **Perceived Susceptibility:**

How much diabetic patients think they might get oral health complications, measured using a Likert scale. (1 = Strongly Disagree to 5 = Strongly Agree). Higher scores reflect a greater perceived susceptibility. Pre and post intervention scores were compared, with cutoff levels based on the mean  $\pm$  SD. (7)

### **Perceived Severity:**

Participants' perceptions of the severity of oral health complications and their potential impact on their overall wellbeing and diabetes management. Assessed through Likert scale statements rated from 1 (Strongly Disagree) to 5 (Strongly Agree). Higher scores indicate greater perceived severity. Pre and post scores will be compared using the mean and SD as cutoff criteria.(7)

### **Perceived Benefits:**

Participants' beliefs about the positive outcomes of engaging in oral hygiene behaviors, such as prevention of oral complications. Assessed using Likert-scale items from 1 (Strongly Disagree) to 5 (Strongly Agree). Higher scores reflect

stronger perceived benefits. Pre and post intervention scores will be compared, and categorization will be done using the mean and SD. (7)

**Perceived Barriers:**

Perception of participants about different challenges that hindered their ability to maintain proper oral hygiene. These self-reported barriers consist of financial constraints, time constraints, and insufficient knowledge or awareness about oral health care. Measured using items rated from 1 (Strongly Disagree) to 5 (Strongly Agree). Higher scores represent greater perceived barriers. Pre- and post-scores will be compared, with cutoffs based on mean  $\pm$  SD. (7)

**Self-Efficacy:**

Confidence in performing and maintaining oral hygiene behaviors. It will be assessed via Likert scale items scored from 1 (Strongly Disagree) to 5 (Strongly Agree). Higher scores indicate greater self-efficacy. Pre- and post-intervention results will be compared, with cutoff scores determined by mean and SD. (7)

**Cues to Action:**

Factors which include both Internal and external that motivate participants to involve in oral hygiene behaviors, such as family encouragement or healthcare provider advice. Assessed using a Likert scale. Higher scores denote stronger cues to action. Comparison of pre and post scores were done using the mean and SD for cutoff classification. (7)

**Awareness:**

The participant's knowledge about the relationship between diabetes and oral health issues, assessed through binary questions (Yes = 1, No = 0). Higher scores reflect higher awareness levels. Pre and post awareness scores will be compared, and cutoff scores will be calculated using the mean and SD. (7)

### **Health Belief Model Constructs:**

A theoretical framework which consists of perceived susceptibility, severity, benefits, barriers, self-efficacy, and internal and external cues to action, used to explain and predict oral hygiene behaviors.(7)

## **CHAPTER 2**

### **REVIEW OF LITERATURE**

In relation to the oral health status among individuals with diabetes, Oktawati et al. (2024) observed that nearly half of individuals with diabetes presented with poor oral hygiene, with many diagnosed with gingivitis or periodontitis. Improved periodontal status was directly correlated to better oral health knowledge, which emphasizes the essential role of awareness in managing oral health among individuals with diabetes.(3) Sairat and Phoosuwan (2024) also reported poor oral health behaviors in individuals with diabetes , with an average Decayed, Missing, and Filled Teeth (DMFT) index of 10.6 and irregular tooth brushing. They found that higher oral health literacy, positive attitudes, and regular visits to the dentist were associated with improved behavior.(2)

A scoping review was done by (Poudel et al., 2022) who explored oral health knowledge and practices of individuals with diabetes in South Asia based on literature search from January 2000 to December 2021. Many participants did not know about the relationship between diabetes and oral health and reported that general practitioners do not provide enough information about oral health. This highlights the necessity of awareness raising initiatives. Furthermore, the participants stated that they would want to know more about oral health, especially from medical professionals like dentists and doctors. This review highlights the importance of making oral health education a fundamental part of diabetes care.(11)

Khan et al. (2022) investigated the relationship between poor oral health and patients with T2DM in Pakistan. They found a significant connection between poor oral health and uncontrolled blood glucose levels as well as longer duration of disease. The study highlighted the need to improve oral health awareness and management in this population.(4) A cross-sectional descriptive survey, conducted by (Islam et al., 2021) through self-administered questionnaires on 400 participants with

diabetes at Abbasi Shaheed Hospital, which is the largest government hospital in Karachi, Pakistan revealed that the connection between diabetes and periodontal disease were not well understood by participants. Several participants did not practice recommended oral hygiene practices, such as brushing and flossing. A significant number visited dentists only rarely, due to their busy schedule or financial difficulties. Most participants prefer Television for information related to risk factors, to maintain good health. In order to improve diabetic patients' knowledge and awareness of periodontal risk and encourage good oral health practices, the study highlights the need for targeted educational interventions. (12)

Barriers to providing comprehensive oral health care for individuals with diabetes has also been addressed by Poudel et al. (2020) who found out in his research that while general practitioners know the importance of oral health, their involvement was often limited to encouraging dental appointments and basic recommendations. Challenges such as time limitations, complicated referral processes, and insufficient training hindered effective collaboration between general practitioners and dental professionals. The study suggested that simplified referrals and improved training can better integrate oral health into diabetes management.(13)

Oral health and Diabetes are closely related, making targeted interventions important to address oral health problems in this population. Malekmahmoodi et al. found that an educational intervention based on the HBM improved oral hygiene practices among individuals with T2DM, with the intervention group showing statistically significant improvements as compared to the control group.(7) Similarly, Sowmya and Sangavi (2024) reported a 61% improvement in oral health outcomes after oral health education intervention, highlighting the value of educational programs in providing comprehensive care for individuals with diabetes.(5)

Building on these findings, Haghdoost et al. demonstrated that social media-based interventions were better than traditional pamphlet or routine-based methods in enhancing oral health awareness.(10) Regardless of patients' health literacy levels, diabetes education through WhatsApp showed promising results, according to a randomized, two-arm parallel interventional study conducted by Al Omar, Hasan, Palaian, & Mahameed, in 2020 with a 6-month patient follow-up that evaluated the effect of a patient centered diabetes education program delivered via WhatsApp on glycosylated hemoglobin (HbA1c) values. (14)

Extending the discussion of interventions, Mesbahi and Aleksejuniene (2024) used the HBM to guide an SMS based reminder strategy aimed at improving oral health behaviors among adolescents. This intervention, comprising educational sessions and text message reminders, significantly enhanced oral self-care practices and increased duration of tooth brushing. A 100% participation rate underscored the feasibility and acceptability of this approach.(9)

In spite of the well-recognized oral health challenges faced by individuals with diabetes, there are noticeable gaps in Pakistan to address these challenges. The lack of awareness and poor adherence to oral health practices among individuals with diabetes has been documented in researches like that of Islam et al., 2021 and Khan et al. (2022).(4,12) Despite this, very few studies offer actionable strategies to improve oral health behavior among people with diabetes. Theory based interventions like HBM, have proven effective in shaping health interventions globally, but they are seldomly used for oral health education in Pakistan. Using WhatsApp, a widely accessible and familiar platform, this study aims to fill the gaps by encouraging lasting improvements in oral health behaviors among individuals with diabetes.

## CHAPTER 3

